2.0 INTRODUCTION: BACKGROUND INFORMATION & SCIENTIFIC RATIONALE

2.1 Introduction/Rationale for Development

Tetrahydrocannabivarin (THCV) is a rare cannabinoid and is a homologue of THC that differs only in the length of the alkyl side chain (3C vs 5C, respectively). Pre-clinical and clinical trials have shown that THCV has medical potential as a neuroprotectant, anti-inflammatory, anti-anxiety, and most notably as a therapeutic to improve glycemic control in type 2 diabetic patients.

Several THCV products are available in states with recreational cannabis. Anecdotal reports from adult cannabis users indicate that THCV provides an energizing, focusing and euphoric high—while still creating a lucid, uplifting experience. Additionally, unlike THC-dominant products, THCV was not reported to increase appetite. Other anecdotal comments referring to increased ability to focus for long periods of time and being more active were common.

Given anecdotal evidence, which shows that THCV is activating and improving focus, this provides rationale and justification to conduct a clinical research study to further test and

understand whether THCV improves motivation, focus, level of energy, and does not stimulate appetite in healthy adults.

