3.2 Eligibility

Participants must meet all of the following criteria on screening to be considered eligible to participate in the study:

Inclusion Criteria

1. Healthy adults age \geq 21 years old
2. Work / study / play in an environment that requires focus
3. Able to read and understand English
4. Able to read, understand, and provide informed consent
5. Able to use a personal smartphone device and download Chloe by People Science
6. Able to complete study assessments over the course of up to 14 days
7. Familiar with the use of cannabis and its effects
8. Able to tolerate at least 5mg THC
9. Willingness to abstain from use of any THC containing products during study product use days
10. Willingness to abstain from use of alcohol during study product use days

11. Greater Los Angeles area residents only

Exclusion Criteria

1. Participants who do not have a smartphone and/or internet access
2. Any known adverse effects from taking cannabis
3. Concomitant Therapies: Currently taking medication for ADHD or psychotropic medications
4. Other Illnesses or Conditions: Participants who have the following co-morbidities are excluded:
 - a. History or currently undergoing product use for substance abuse disorders
 - b. Currently pregnant, planning to become pregnant within the next month, or breastfeeding
 - c. Allergies to formulation ingredients
 - d. Current or prior psychotic disorder
 - e. Immunosuppressive product uses, including organ transplant participants, active immunotherapy for cancer product use
 - f. Any condition that is considered by investigator to be a contraindication to cannabis (e.g. specific drug-use interaction, unstable cardiac arrhythmia)

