3.4 Participant Recruitment

Participants will be recruited through the People Science community, People Science website, email outreach and social media channels, in addition to Phylos' community network. Local dispensaries may also be used for recruitment purposes, as deemed appropriate by Phylos and People Science. Advertisements will be in digital format and will link to a study landing page to enable sign up.

Interested individuals will have already made the decision to try these cannabinoid products.

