6.0 STUDY PROCEDURES

6.1 Study Overview

Upon initial qualification, the participant will receive an email with study onboarding information including instructions to complete study assessments, as required. These study assessments can be accessed via the Chloe mobile app available on Apple iOS and Android devices. The participant's activities are as follows:

Screening Day -14 to Day 0:

- Complete the Informed Consent
- Complete Demographics, Medical History and Concomitant medications, including current cannabis use information (frequency, route, any previous adverse reactions from taking cannabis and tolerance in taking at least 5mg THC previously)
- Eligibility Confirmation and Enrollment

Baseline Day 1 to Day 14:

- Provide preferred delivery address for product delivery during Baseline
- Random assignment to either Study Product, THC-Only Product, or Placebo Group
- MEFA Questionnaire
- Receipt of study products within 2 weeks of eligibility confirmation
 - Participants will be asked daily if they have received their study product delivery
 - Once they confirm receipt, they will be advised on the product use period start date

Product Use Period (Up to 21 days):

- *The Participant will be randomized into either Study Product, THC-Only Product, or Placebo Group upon enrollment*

- *The Participant will be crossed-over twice into the Study Product, THC-Only Product, or Placebo Group once they have completed 3 product use sessions during the first and second product use periods*
- *The Participant will complete a total of 9 product use sessions between Study Product, THC-Only Product, and Placebo groups across a maximum of 21 days*
- *The Study Product will contain 10mg THCV + 5mg THC in the form of a single gummy.*
- *If the participant cannot tolerate or is not comfortable with 10mg THC based on cannabis use information collected at screening, the participant may opt to cut the gummy in half and be advised to use the same dose for all product use days for the duration of the study.*

Period 1: Up to 7 days

- After 3 product use sessions:
 - Daily survey questions regarding motivation, level of energy, focus and appetite
 - At the end of Period 1:
 - MEFA Questionnaire and Adverse Event Reporting

Crossover:

- Upon completion of Period 1, participants will cross-over to either the Study Product, THC-Only Product, or Placebo group for up to 7 days.

Period 2: Up to 7 days

- After 3 product use sessions:

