10.0 STUDY COMPLIANCE AND REPORTING OF DEVIATIONS FROM APPROVED PROCEDURES

Deviations

A deviation is a divergence from a specific element of a protocol and that occurred without prior IRB approval. Deviations from the approved protocol should be avoided, except when necessary to eliminate an immediate hazard to a research participant. All deviations from the protocol will be documented in study source documents and promptly reported to the IRB.

Reporting Deviations

Investigators may deviate from the protocol to eliminate immediate hazards for the protection, safety, and well-being of the study subjects without prior IRB approval. For any such deviation, the PI will notify the IRB, within 5 calendar days of its occurrence by electronic submission of a deviation notice.

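### Inclusion criterion 9 bars only THC-containing products on session days, so THC-free THCV is permitted on placebo and THC-only days and could dilute the product contrasts

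*Combined protocol and SAP*

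**What the plan says.** Section 3.2 has two abstention criteria. Criterion 9 is "Willingness to abstain from use of any THC containing products during study product use days" and criterion 10 is "Willingness to abstain from use of alcohol during study product use days". Both are statements of willingness checked at screening. No exclusion criterion mentions THCV, CBD or any other cannabinoid without THC.

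Section 6.1 gives the test product: "The Study Product will contain 10mg THCV + 5mg THC in the form of a single gummy". The other two conditions are a THC-only product and placebo, so THCV is what distinguishes the Study Product from the THC-only product. Section 2.1 names the effect of THCV on motivation, focus, energy and appetite as the question, and notes that "Several THCV products are available in states with recreational cannabis". Section 3.4 adds that "Local dispensaries may also be used for recruitment purposes".

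Cannabis use is recorded at screening (Section 6.1: "Complete Demographics, Medical History and Concomitant medications, including current cannabis use information"). The calendar in Section 4.0 likewise shows concomitant medications at screening only. The daily survey is described as covering motivation, energy, focus and appetite.

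Section 10.0 defines the term: "A deviation is a divergence from a specific element of a protocol".

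**The concern.** The rule restricts the background ingredient and leaves the test ingredient open. A participant who takes a THC-free THCV product on a placebo or THC-only day has followed the protocol as written.

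That matters for the between-product comparisons. Section 1.0 defines the primary endpoint as cannabinoid products against placebo sessions. Section 9.1 analyses the differences among the three groups, and Section 9.6 tests the difference in VAS change between them. Outside THCV on a comparator day would be expected to move that day's rating towards the Study Product rating and so shrink the contrast.

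Because such use is permitted and no per-session record of it is described, the analyst could neither count affected sessions nor set them aside. This cannot be repaired after data collection.

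**Working it through.** **1. Does any other text close the gap?**

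| Place | Covers THC-free THCV on session days? |
|---|---|
| Section 3.2, inclusion 9 | No; THC-containing products only |
| Section 3.2, inclusion 10 | No; alcohol only |
| Section 3.2, exclusions | No; medications, illnesses, allergies, pregnancy, contraindications |
| Section 4.0, calendar | No; no entry for outside cannabinoid use during product use |
| Section 6.1, procedures | No; cannabis use asked at screening |
| Section 7.1, data elements | Lists medications and supplements, but the calendar shows no collection during product use |
| Section 10.0, deviations | Needs a specific protocol element to diverge from; none applies |

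The gap stands. It is limited to THC-free products, because a product with both THCV and THC is already barred by criterion 9.

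**2. The plan's own power figure.** Section 9.6 gives a mean change of 1 point, SD 2, two-sided 0.05, the Wilcoxon signed-rank test, at least 90% power and up to 58 participants. Section 9.1 expects about 50 evaluable.

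- Normal approximation: n = [SD × (z0.975 + z0.90) / δ]² = [2 × (1.960 + 1.282) / 1]² = 42.03, so 43. The t-based figure is 44.
- Wilcoxon with normal data has relative efficiency 3/π = 0.955. This gives 42.03 / 0.955 = 44.01, so 45 (47 from the t-based figure: 44 / 0.955 = 46.08).
- Wilcoxon power, using noncentral t with effective size n × 3/π: 92.3% at n = 50 and 95.5% at n = 58.

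The stated figure reproduces.

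**3. Illustration of dilution.** The documents give no rate of outside use, so four things are assumed:

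- a fraction f of comparator sessions includes outside THCV;
- that THCV carries the full Study Product effect;
- the 1 point and SD 2, stated in Section 9.6 for change from baseline, apply to the between-product contrast;
- the SD of the paired difference stays at 2.

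The contrast becomes 1 × (1 − f) and the standardised effect 0.5 × (1 − f). The noncentrality is 0.5 × (1 − f) × √(n × 3/π). For n = 50, √47.75 = 6.910; for n = 58, √55.39 = 7.442.

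| f (assumed) | Contrast | Noncentrality, n = 50 / 58 | Wilcoxon power, n = 50 / 58 |
|---|---|---|---|
| 0% | 1.00 | 3.46 / 3.72 | 92.3% / 95.5% |
| 5% | 0.95 | 3.28 / 3.53 | 89.5% / 93.5% |
| 10% | 0.90 | 3.11 / 3.35 | 86.1% / 90.8% |
| 20% | 0.80 | 2.76 / 2.98 | 77.2% / 83.2% |
| 30% | 0.70 | 2.42 / 2.60 | 65.9% / 72.5% |

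Simulation with 20,000 trials per setting agrees to within one percentage point. Under this model, power drops below 90% at f of about 5% with 50 participants and about 12% with 58.

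**4. Partial effect.** THC-free THCV on a placebo day can reproduce only the THCV part of a THCV-plus-THC effect. If that part is a share h of the whole, the contrast is 1 − f × h. With h = 0.5 (assumed) and f = 20%, it is 1 − 0.10 = 0.90, which is the 10% row (86.1% / 90.8%) and not the 20% row. The table is therefore an upper bound on the loss, provided that outside THCV acts no more strongly than the Study Product.

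**The case against.** The strongest reply is that the documents do not show the exposure. Section 2.1 says that THCV products are sold but not that any is free of THC, and the only THCV product whose contents are described contains THC. A reader might also take "Interested individuals will have already made the decision to try these cannabinoid products" in Section 3.4 as a sign that participants use THCV of their own. The sentence most naturally means the study's products, as the similar sentence in Section 2.2 does, and it says nothing about outside use during the study. Possible dispensary recruitment suggests access to cannabis shops, not a rate of use. All of this stands, so dilution is a possibility and not a finding.

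Second, the power figures borrow planning values from another comparison. The test powered in Section 9.6 compares pre-use with post-use scores, where comparator-day use does not act in the same way. No effect size, SD or power is given for Study Product against THC-only. This also stands, and the figures are illustrative for that reason. It does not remove the point: Sections 1.0 and 9.1, and the group comparison in Section 9.6, all rest on between-product differences. The mismatch between Section 1.0 and the powered test is a separate matter to reconcile.

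Third, rewording alone would not make outside use visible, because the criterion is a willingness statement at screening. This is correct, and the fix therefore includes a per-session record.

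Finally, the full survey and app wording are not in the documents, so participants may be told or asked more than the protocol shows. If so, the protocol should say it.

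**Conclusion.** The wording gap is real and nothing else in the protocol closes it: the ingredient under test is permitted, in THC-free form, on placebo and THC-only days. Such use would not be a deviation under Section 10.0 and could dilute the between-product contrasts.

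A reader might go further and infer that the contrast will be diluted, or that the trial's power is in fact below 90%. The documents support neither. They give no rate of use and do not show that THC-free THCV products are available, and the stated power reproduces on its own terms. Nor does every outside cannabinoid dilute: CBD and others could add noise or bias in either direction.

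The size is thus conditional. At 10% of comparator sessions affected, the upper-bound model takes power to 86.1% with 50 participants, while 58 would still give 90.8%. This is an inexpensive improvement to the design, not an error in a stated figure.

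**What to change.** - Reword inclusion criterion 9 to: 'Willingness to abstain from any cannabis or cannabinoid product (including THC, THCV and CBD) other than the assigned study product during study product use days'.
- Repeat that instruction in the participant-facing material for the product use periods.
- Add one question to the existing Daily Product Use Survey asking whether any non-study cannabinoid product was used that day.
- State in Section 9.6 a sensitivity analysis of the between-product contrasts that excludes affected sessions.

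The cost is one survey item and a short wording change. A few regular users of non-THC cannabinoids may decline to take part. Sample size, product and session schedule do not change.

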3.3 Duration of Participation and Overview of What is Expected from Participants

Participants will complete up to a seven week study consisting of screening period, baseline period, up to a 21-day product use period with a total of 9 product use sessions. Screening assessments, baseline questions, product use period questionnaires, adverse event reporting, and end of study experience survey data will be collected. This study will be conducted remotely and will use a web-based data collection platform, Consumer Health Learning and Organizing Ecosystem (Chloe), by People Science where participants will complete study assessments using the Chloe app during the course of the study. Participants will receive the study product during the baseline period. Demographic and medical history data will be collected for the study.

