4.0 STUDY ACTIVITY CALENDAR

Table 4.1 Study Calendar

| Protocol Activities | Screening ^(a) | Baseline ^(b) | Study Duration | | | | | | | | |
|---|--------------------------|-------------------------|---|-----------------------|------------------------------------|---|-----------------------|------------------------------------|---|-----------------------|---|
| | | | Product Use Period 1 ^(c) (Up to 7 Days) | | | Product Use Period 2 ^(c) (Up to 7 Days) | | | Product Use Period 3 ^(c) (Up to 7 Days) | | |
| | Up to Day -14 | Up to Day 14 | Product Use Session 1 | Product Use Session 2 | Product Use Session 3 / Cross-Over | Product Use Session1 | Product Use Session 2 | Product Use Session 3 / Cross-Over | Product Use Session1 | Product Use Session 2 | Product Use Session 3 / End of Study ⁽ⁱ⁾ |
| Informed Consent | X | | | | | | | | | | |
| Medical History | X | | | | | | | | | | |
| Demographics | X | | | | | | | | | | |
| Concomitant Medications | X | | | | | | | | | | |
| Eligibility Confirmation | X | | | | | | | | | | |
| Product Delivery Receipt | | X | | | | | | | | | |
| Randomization ^d (Study Product, THC Only Product, or Placebo Group) | | X | | | | | | | | | |
| MEFA Questionnaire ^e | | X | | | X | | | X | | | X |
| Daily Product Use Survey ^f | | | X | X | X | X | X | X | X | X | X |
| Adverse Event Survey ^g | | | X | X | X | X | X | X | X | X | X |
| Cross-Over ^h (Study Product, THC Only, or Placebo Group) | | | | | X | | | X | | | |
| Experience Survey | | | | | | | | | | | X |

- a. Screening activities to occur within 14 days prior to Baseline (Day -14).
- b. Baseline activities to occur up to 14 days prior to study product use sessions (Day 14).
- c. Study duration to take place up to 21 days total across 7 days maximum within 3 periods.
- d. Participants to be randomized into the Study Product, THC-Only Product, and Placebo groups for each Product Use Period.
- e. MEFA (Motivation, Energy Level, Focus, and Appetite) Questionnaire to be administered during Baseline and at the end of Product Use 3 sessions.
- f. Daily Product Use Surveys to be administered at the end of each product use session.
- g. Any adverse event occurrence to be reported after the product use session.
- h. Participants cross-over into either Study Product, THC-Only Product, or Placebo group upon completion of Product Use Period 1 and 2.
- i. Participants to complete an experience survey at the end of the study.

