12.3 Participant Characteristics

Research equity

This research has no direct exclusions related to gender. There are also no direct exclusions related to race or ethnicity.

Vulnerable Populations

Pregnancy and lactation are exclusions due to the unknown risks of cannabis product use to fetuses and newborns.

Volunteers with impaired decision-making capacity are excluded.

Volunteers unable to personally provide informed consent (including but not exclusive of inability to speak and read English, hearing or sight impaired, etc.) will be excluded from participating in this research.

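### The pregnancy-planning exclusion looks one month ahead from screening, but the permitted schedule lets product use run to day 35 after eligibility confirmation (day 49 after screening starts)

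*Combined protocol and SAP*

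**What the plan says.** Section 3.2 sets the time at which eligibility is judged: "Participants must meet all of the following criteria on screening to be considered eligible to participate in the study". Exclusion 4b in that list reads "Currently pregnant, planning to become pregnant within the next month, or breastfeeding". It does not say from which day the month is counted.

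Table 4.1 marks eligibility confirmation in the screening column only. None of its later activities is identified as a pregnancy question or test.

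The schedule that follows is given in three places:

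- Section 3.3: "Participants will complete up to a seven week study consisting of screening period, baseline period, up to a 21-day product use period".
- Section 6.1, baseline: "Receipt of study products within 2 weeks of eligibility confirmation". Section 6.1 also places eligibility confirmation within screening, Day -14 to Day 0.
- Section 6.1, product use: participants "complete a total of 9 product use sessions between Study Product, THC-Only Product, and Placebo groups across a maximum of 21 days".

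Section 12.3 gives the reason for the related exclusions: "Pregnancy and lactation are exclusions due to the unknown risks of cannabis product use to fetuses and newborns".

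Inclusion criterion 6, in the same list as 4b, reads "Able to complete study assessments over the course of up to 14 days". That is shorter than the 21-day product use period alone.

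**The concern.** A criterion about planned pregnancy protects participants only if its look-ahead covers the time during which they take the product. Here the question is asked once, before a delivery wait and three use periods, and it looks only one month ahead. A volunteer could truthfully answer that she has no plan to conceive in the next month, be admitted, and reach her intended start date while sessions remain.

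What is at stake is participant protection, not inference. Section 12.3 cites unknown fetal and newborn risk as the reason for excluding pregnancy and lactation. It does not mention planned conception, so the link to 4b is inferred from that rationale and from the fact that 4b looks ahead at all. The point does not concern unplanned pregnancy.

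**Working it through.** **Inputs**

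- Maximum screening: 14 days (Table 4.1, footnote a).
- Maximum baseline and delivery: 14 days (Table 4.1, footnote b; section 6.1).
- Maximum product use: 3 periods × 7 days = 21 days (Table 4.1, footnote c).
- Look-ahead: one month, taken as 28, 30 or 31 days because the protocol gives no length in days.

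**Reproducing the plan's own figure.** 14 + 14 + 21 = 49 days = 7 weeks, which matches the maximum participation stated in section 3.3. The longest schedule is therefore one the protocol plans for.

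**Last possible product use**

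- From eligibility confirmation: 14 + 21 = day 35, with product use on days 15 to 35.
- From the first day of screening, if confirmation comes at the end of screening: 14 + 14 + 21 = day 49, with product use on days 29 to 49.

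**Shortfall = last-use day − length of the month**

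| Month | Counted from eligibility confirmation | Counted from first day of screening |
|---|---|---|
| 28 days | 35 − 28 = 7 days | 49 − 28 = 21 days |
| 30 days | 35 − 30 = 5 days | 49 − 30 = 19 days |
| 31 days | 35 − 31 = 4 days | 49 − 31 = 18 days |

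**Sessions outside the window.** Each participant has 9 sessions, 3 of them placebo, so 9 − 3 = 6 are with active product.

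- From eligibility confirmation, Period 3 is days 29 to 35, so all uncovered days lie in that period. At most 3 of 9 sessions are uncovered. Period 3 may be the placebo period, so between 0 and 3 of the 6 active sessions are uncovered.
- From the first day of screening, a 31-day month covers only days 29 to 31 of Period 1. At one session a day (an assumption) that is at most 3 sessions, leaving 6 to 9 of 9 uncovered, including 3 to 6 of the 6 active ones. A 30-day month leaves 7 to 9 uncovered. A 28-day month ends before first use and leaves all 9.

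**When the gap opens.** With the full 21 days of use, the month is long enough only if the delay from the 4b answer to the start of use is no more than month − 21: 28 − 21 = 7 days to 31 − 21 = 10 days. The protocol allows 14 days from eligibility confirmation, and 28 from the start of screening.

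**A fast schedule.** If the nine sessions take nine days (the same one-a-day assumption), last use is day 14 + 9 = 23 from eligibility confirmation, and there is no gap. From the first day of screening it is 14 + 14 + 9 = day 37, still past 31.

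**If product use lasted 14 days,** as inclusion criterion 6 might suggest, last use would be day 14 + 14 = 28 from eligibility confirmation, inside the month. From the first day of screening it would be 14 + 14 + 14 = day 42, outside it.

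**The case against.** The arithmetic is not in dispute; the weight is. Counted from eligibility confirmation, harm needs several things together: delivery close to its limit, use stretched past day 28 to 31, a plan to conceive that starts in the uncovered days, and a participant who keeps taking the product anyway. She may withdraw at any time (section 12.6), and the uncovered sessions may all be placebo. This is fair, and it is why the point is small. It does not show that the criterion covers the schedule the protocol permits.

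Day 49 is the weaker figure. It needs 4b answered on the first day of a full screening period with confirmation at the end. Section 6.1 ties delivery to confirmation, so an earlier confirmation also brings the delivery deadline forward. This stands: day 35 is the main figure and day 49 the outer bound.

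Criterion 6 may suggest that the eligibility list was not updated when the calendar was lengthened. That is consistent with the text but not shown by it. Criterion 6 speaks of assessments rather than product use, and a 14-day use period fits the month only when counted from confirmation. The conclusion does not rest on it.

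The consent pages are not available, and they may contain instructions on avoiding pregnancy or stopping use. That is possible, so 4b may not be the only safeguard. Consent wording would still leave unchanged the criterion that decides who is admitted.

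Finally, the month might be meant to run from first use. The text does not say so, and stating it would itself require an edit.

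**Conclusion.** The concern holds. As written, the look-ahead in 4b can end before the last product use: by 4 to 7 days counted from eligibility confirmation, and by 18 to 21 days at the outer bound. This assumes a month of 28 to 31 days, the maximum delivery and use periods, and no later check beyond those in Table 4.1. On shorter schedules the gap narrows or vanishes. The documents do not allow an estimate of how many of the roughly 58 participants would be affected, and the number may be very small. It should be corrected because the criterion falls short of its evident purpose and the correction is cheap, not because it threatens the trial's results.

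**What to change.** Reword that part of exclusion 4b, and the matching screening question, to cover *plans for pregnancy at any time during study participation, through the last product use session*. This closes the gap on every schedule.

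Two alternatives also work:

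- A fixed window of at least seven weeks from the start of screening. This is broader than needed for volunteers who finish early.
- Repeating the question at product receipt. The 21 days of use then fit within a month provided use starts within 7 to 10 days. This adds one question to the baseline activities.

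In the same edit, check the 14 days in inclusion criterion 6 against the 21-day product use period. The cost of the main fix is one line in the criterion and in the screening question, and possibly a few more volunteers excluded.
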